**Table 10: Amendment 3 Summary of Changes**

Section(s)	Change	Rationale
4.1 Overall Design, 6.4 Measures to Minimize Bias, 9.2 Sample Size Determination	Randomization ratio changed from 1:1 to 2:1 (dociparstat: placebo) for Phase 2 Cohorts 2 and 3 and for Phase 3. Phase 2/Cohort 3 sample size adjusted from N=50 to N=51 (34 dociparstat and 17 placebo) and Phase 3 adjusted from N=452 to N=450 (300 dociparstat and 150 placebo).	To increase the number of participants with COVID-19 who are exposed to dociparstat. The number of participants was adjusted to align with the change in randomization ratio.
9.4 Statistical Analyses, 9.6 Data Monitoring Committee	Modified text to indicate the sponsor may decide to unblind and review study data following Cohort 1 and/or 2 (previously only after Cohort 2).	Based on the slower than anticipated study enrollment and the rapidly evolving COVID-19 landscape, the sponsor wants the flexibility to review unblinded data after completion of Cohort 1. This change is being included in this amendment from an administrative change letter issued 28 September 2020.
9.5 Phase 3 Interim Futility Analysis, 9.6 Data Monitoring Committee	Timing of futility analysis and DMC safety review adjusted from after 226 participants complete the study to after 225 participants complete the study.	To align with change in randomization ratio and sample size adjustment.

1. PURPOSE

This is a randomized, double-blind, placebo-controlled, Phase 2/3 study to determine the safety and efficacy of dociparstat in adults with acute lung injury associated with severe COVID-19 who are at high risk of respiratory failure.

An independent unblinded data monitoring committee (DMC) will review safety data from Cohort 1 to make a recommendation on dose escalation in Cohort 2 and review safety data from both Cohorts 1 and 2 to make a recommendation on dosing in Cohort 3. The sponsor will consider the DMC recommendation when determining the actual doses for Cohorts 2 and 3.

Due to the evolving standard of care for COVID-19, the sponsor may decide to unblind and review study data following Cohorts 1 and/or 2.

The purpose of this document is to describe the pre-defined post-Cohort 1 or 2 lock analysis. This document specifies the derivations and TFL package and is based on the study protocol amendment 3, dated 06 November 2020.

2. INTRODUCTION

Cohort 1 contains 6 participants randomized to dociparstat, 6 randomized to placebo. Dociparstat will be dosed as 4 mg/kg IV bolus followed by continuous infusion of 0.25 mg/kg/hr.

Cohort 2 includes 6 participants randomized to dociparstat, 6 randomized to placebo. Dociparstat will be dosed as 4 mg/kg IV bolus followed by continuous infusion of 0.325 mg/kg/hr (dose to be confirmed after review of data from Cohort 1).

Based on Protocol Amendment 3, dated 06 November 2020, the randomization ratio (dociparstat: placebo) changed from 1:1 in Cohort 1 to 2:1 in the following cohorts.

Both Cohorts 1 and 2 may be unblinded to the entire team following cleaning and database lock of Cohort 1/2 data. The full randomization code will remain blinded as is; in this event, only the Cohort 1/2 assignments will be unblinded.

The first part of the analysis defined in this document will be equivalent to the statistical output delivered to the DMC-members for the 2nd Cohort (see Section 5.1), however with all data collected until End of Study (EOS).

3. DERIVATIONS AND DEFINITIONS

Kaplan-Meier estimates

Time to xxx (days): Days are calculated as (start date/time – first study drug date/time)/24h). Time will be censored at last individual date/time reported.

Worst-case results in 2 scenarios for missing time-values:

1. Missing time for negative events will be imputed with “00:01”, missing time for censored observations will be imputed with “23:59”.

Negative events are:

- Time to first invasive mechanical ventilation or ECMO
- Time to first invasive mechanical ventilation, ECMO or all-cause mortality
- Time to all-cause mortality

2. Missing time for positive events will be imputed with “23:59”, missing time for censored observations will be imputed with “00:01”.

Positive events are:

- Time to clinical improvement
- Time to hospital discharge

In addition, to avoid bias in the positive events, deaths occurring prior to the positive event being observed will be censored at Day 28.

Ventilator-free days

Ventilator-free days are only counted from baseline through Day 28 or end of study, whichever comes first. They are derived based on the eCRF data collected on the Ventilator/Oxygen/Medical Care Status CRF page, Ventilator-free days are all days where Ventilator/Oxygen/Medical Care Status is not equal “Invasive Mechanical Ventilation or extracorporeal membrane oxygenation (ECMO)”.

Ventilator days are defined as cumulative rounded number of days with Ventilator/Oxygen/Medical Care Status = “Invasive Mechanical Ventilation or extracorporeal membrane oxygenation (ECMO)” divided by 24 h. Missing time for start will be imputed with “00:01”, missing time for stop will be imputed with “23:59”.

Study duration in days is defined as: Date of study completion (or date of early study discontinuation) – date of first study treatment + 1. For subjects randomized but not treated the date of randomization will be used instead of first study treatment date. The maximum study duration is set to 28 days, even if study completion or study discontinuation is after 28 days.

Ventilator-free days are defined as: study duration - number of ventilator days. For subjects who died during the course of the study, the number of ventilator-free days will be defined as 0.

Randomized, but not treated subjects:

The following rules will apply for randomized subjects without receiving study treatment, if not stated otherwise:

- Calculations referring to start of treatment or baseline will be performed with respect to randomization date/time.
- Study duration in days is calculated as study discontinuation date - randomization date +1.
- In Kaplan-Meier analysis the “time-to” will be censored at 0.

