**Figure 1: Treatment Algorithm**

## 1.1. Schedule of Activities

**Table 1: Schedule of Activities/Assessments**

Study Day:	Screen	BL/ D1	D 2	D 3	D 4	D 5	D 6	D 7	D 8	D 14±3d	D 28±3d	Early Therapy DC	Notes
Examination / Procedure													
Informed consent	X												Study day is relative to Day 1= first dose of study intervention
Eligibility criteria	X	X											
Demographics	X												
Medical history	X	X											
Physical examination / vital signs	X												Record abnormal results as medical history
Height / Weight	X												
Temperature / antipyretic use	X	X	-----→								X		Collect per standard of care through hospital discharge
Electrocardiogram a	X			X									Monitor per standard of care
Pregnancy test (as applicable)	X												Women of childbearing potential
Laboratory assessments – Hematology, Clinical chemistry b – D-dimer, fibrinogen	X	X	X		X		X		X	X	X		Local laboratory – record results in the case report form
– Biomarkers (e.g., HMGB1, IL-6, SAA, TNF $\alpha$ )		X	X	X	X	X	X	X	X	X	X		Store plasma samples for central laboratory analysis
– PT/INR, aPTT c,d	X	X	X	X	X	X	X	X				X	Local Lab. Do not draw from the same line used for drug administration c,d
– Anti-Xa (if applicable)		X	X	X	X	X	X	X				X	To monitor enoxaparin anticoagulation
Pharmacokinetic samples (sites with appropriate capabilities)		X c	X c		X c				X c				D1 predose and end of bolus dose, D2 and D4 anytime, D8/end of continuous infusion. Do not draw from the same line used for drug administration. Central laboratory analysis.
NIAID ordinal scale components – Ventilator use – Oxygen use	X	X	-----→								X		Record date/time for each change in individual components of the assessment e
Sample for virology		X						X					Cohort 3 and Phase 3 only
Randomization		X											

Study Day:	Screen	BL/ D1	D 2	D 3	D 4	D 5	D 6	D 7	D 8	D 14±3d	D 28±3d	Early Therapy DC	Notes
Examination / Procedure													Study day is relative to Day 1= first dose of study intervention
Study intervention – bolus dose		X											
Study intervention – continuous infusion – start/change IV bag		X	X	X	X	X	X	X	End				Begin after bolus dose
Adverse event assessments f	Procedure-related SAEs	X	-----→								X		Record through Day 28
Concomitant medications	X	X	-----→								X		

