#### **4.4. End of Study Definition**

A participant is considered to have completed the study if he/she has completed the Day 28 follow-up visit.

The end of the study is defined as the date of the last visit of the last participant in the study.

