(b) Kaplan-Meier estimates: Subjects who died will be counted as events. All other subjects will be censored. Time to all-cause mortality (days): Days are calculated as (start date/time - first study drug date/time)/24h). Time will be censored at last individual date/time reported. If time is not available for events "00:01" will be imputed, for censored observations "23:59" will be imputed. Randomized untreated subjects will be censored at time = 0.

Page X of Y

(Notes for programmer: Subjects randomized not treated will be counted in

- a) as event (in the line "Early study discontinuation < Day 25") in case of early study discontinuation < Day 25
- b) as censored observation (censor time = 0)

)

Figure 6: Time to all-cause mortality (KM-Plot) - ITT Set

Kaplan-Meier Plot:

y-axis:

range: 0% to 100% by 20%
label: Event-free Probability
reference-line: 50%

x-axis:

range: 0 to xxx (depending on data), by 7 days
label: Time to Event (Days)

Lines:

solid
different colors/line styles for the treatment-groups
starting at (100%/Baseline)
Censored values marked

Footnote:

N = Number of subjects in a specific group; (+) = censored values;

Kaplan-Meier estimates: Subjects who died will be counted as event. All other subjects will be censored.

Time to all-cause mortality (days): Days are calculated as (start date/time - first study drug date/time)/24h). Time will be censored at last individual date/time reported. If time is not available for events "00:01" will be imputed, for censored observations "23:59" will be imputed. Randomized untreated subjects will be censored at time = 0.

*(Notes for programmer: Subjects randomized not treated will be counted as censored observation (censor time = 0)
)*

Table 20: Proportion of participants who are alive, discharged from the hospital, and not using home oxygen - ITT Set

Visit	DSTAT 0.25 N=xxx n (%)	Cohort 1 PBO N=xxx n (%)	DSTAT 0.325 N=xxx n (%)	Cohort 2 PBO N=xxx n (%)
Day 8 (D8)	xx (xx.x)	xx (xx.x)	xx (xx.x)	xx (xx.x)
Day 14 (D14)	xx (xx.x)	xx (xx.x)	xx (xx.x)	xx (xx.x)
Day 28 (D28)	xx (xx.x)	xx (xx.x)	xx (xx.x)	xx (xx.x)

N = Number of subjects in a specific group; n = Number of subjects with data available;

Subjects who discontinued study early prior to start of time window (-3 days to -1 day for each visit) will be considered as failures even if alive and last records indicate no oxygen and out of hospital.

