(a) Subjects with a clinical improvement will be counted as event.

(b) Kaplan-Meier estimates: Subjects with a clinical improvement will be counted as event. Subjects without a clinical improvement or deaths occurring prior to the positive event will be censored. Time to clinical improvement: Days are calculated as (start date/time - first study drug date/time)/24h. Time will be censored at last individual date/time reported. If time is not available for events "23:59" will be imputed, for censored observations "00:01" will be imputed. Participants who died prior to Day 28 without clinical improvement will be censored at Day 28. Randomized untreated subjects will be censored at time = 0.

Page X of Y

(Notes for programmer: Subjects randomized not treated will be counted as censored observation (censor time = 0)
)

Figure 7: Time to clinical improvement (KM-Plot) - ITT Set

Kaplan-Meier Plot:

y-axis:

range: 0% to 100% by 20%
label: Event Probability
reference-line: 50%

x-axis:

range: 0 to xxx (depending on data), by 7 days
label: Time to Event (Days)

Lines:

solid
different colors/line styles for the treatment-groups
starting at (0%/Baseline)
Censored values marked

Footnote:

N = Number of subjects in a specific group; (+) = censored values;

Clinical improvement is defined as at least a 2-grade improvement from baseline on the NIAID ordinal score.

Kaplan-Meier estimates: Subjects with a clinical improvement will be counted as event. Subjects without a clinical improvement or deaths occurring prior to the positive event will be censored.

Time to clinical improvement (days): Days are calculated as (start date/time - first study drug date/time)/24h). Time will be censored at last individual date/time reported. If time is not available for events "23:59" will be imputed, for censored observations "00:01" will be imputed. Participants who died prior to Day 28 without clinical improvement will be censored at Day 28. Randomized untreated subjects will be censored at time = 0.

(Notes for programmer: Subjects randomized not treated will be counted as censored observation (censor time = 0)

)

Table 23: Number of ventilator-free days from baseline through Day 28 - ITT Set

	DSTAT 0.25 N=xxx	Cohort 1 PBO N=xxx	DSTAT 0.325 N=xxx	Cohort 2 PBO N=xxx
Number of ventilator-free days, n(%)				
0	xx (xx.x)	xx (xx.x)	xx (xx.x)	xx (xx.x)
1	xx (xx.x)	xx (xx.x)	xx (xx.x)	xx (xx.x)
2	xx (xx.x)	xx (xx.x)	xx (xx.x)	xx (xx.x)
3	xx (xx.x)	xx (xx.x)	xx (xx.x)	xx (xx.x)

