Time to hospital discharge (days): Days are calculated as (last hospital discharged date/time - first study drug date/time)/24h). Time will be censored at last individual date/time reported. If time is not available for events "23:59" will be imputed, for censored observations "00:01" will be imputed. Participants who died prior to hospital discharge will be censored at Day 28. Randomized untreated subjects will be censored with time to hospital discharge = 0.

(Notes for programmer: Subjects randomized not treated will be counted as censored observation (censor time = 0)
)

Page X of Y

Figure 8: Time to last hospital discharge (KM-Plot) - ITT Set

Kaplan-Meier Plot:

y-axis:

range: 0% to 100% by 20%
label: Event Probability
reference-line: 50%

x-axis:

range: 0 to xxx (depending on data), by 7 days
label: Time to Event (Days)

Lines:

solid
different colors/line styles for the treatment-groups
starting at (0%/Baseline)
Censored values marked

Footnote:

N = Number of subjects in a specific group; (+) = censored values;

Kaplan-Meier estimates: Subjects discharged from hospital will be counted as event. Subjects who are still in the hospital or died in the hospital will be censored.

Time to hospital discharge (days): Days are calculated as (last hospital discharged date/time - first study drug date/time)/24h).

Time will be censored at last individual date/time reported. If time is not available for events "23:59" will be imputed, for censored observations "00:01" will be imputed. Participants who died prior to hospital discharge will be censored at Day 28.

Randomized untreated subjects will be censored with time to hospital discharge = 0.

*(Notes for programmer: Subjects randomized not treated will be counted as censored observation (censor time = 0)
)*

Table 25: Time to first hospital discharge - ITT Set

For the layout refer to Table 24

Adapt footnote:

... Time to hospital discharge (days): Days are calculated as (first hospital discharged date/time - first study drug date/time)/24h)...

Figure 9: Time to first hospital discharge (KM-Plot) - ITT Set

For the layout refer to Figure 8

Adapt footnote:

... Time to hospital discharge (days): Days are calculated as (first hospital discharged date/time - first study drug date/time)/24h)...

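### Deaths leave the discharge and improvement curves at Day 28, but survivors' events can count to Day 31, so a late event is over-weighted in the tail

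*SAP*

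**What the plan says.** SAP Section 3 measures every time-to-event outcome from the first dose and states: "Time will be censored at last individual date/time reported". For the two positive events, clinical improvement and hospital discharge, it adds: "In addition, to avoid bias in the positive events, deaths occurring prior to the positive event being observed will be censored at Day 28".

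The SAP 5.2 table shells repeat the death rule. The footnotes for clinical improvement (Table 22, Figure 7) say: "Participants who died prior to Day 28 without clinical improvement will be censored at Day 28". Those for hospital discharge (Table 24, Figure 8) say: "Participants who died prior to hospital discharge will be censored at Day 28". Table 25 and Figure 9 take their layout from these. None of the footnotes limits a survivor's event to Day 28, and the time axis of the figures is left to depend on the data.

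Follow-up past Day 28 is built into the protocol:

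- The Day 28 visit in the Schedule of Activities has a window of 3 days either side.
- Section 4.4 ties completion to that visit: "A participant is considered to have completed the study if he/she has completed the Day 28 follow-up visit".
- For the ordinal-scale components, the schedule says: "Record date/time for each change in individual components of the assessment". The collection arrow runs to that last visit.

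The SAP's only 28-day cap is on study duration, which is used for ventilator-free days. There it expressly allows for completion after 28 days.

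For mortality, Table 19 footnote (b) says: "Subjects who died will be counted as events. All other subjects will be censored". The event-count rows of Tables 18 and 19 have no closing date for ventilation or death, although the first row of Table 18 runs through Day 28.

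**The concern.** The death rule has a sound purpose. A participant who dies can no longer be discharged or improve, so censoring at the date of death would treat that participant as if the event were still to come. Keeping the dead in the risk set prevents this, but only if they stay in for as long as anyone else's event can count.

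Here two horizons apply within one curve: Day 28 for the dead and the last reported date for everyone else. Between the two, the rule stops doing its job. The protocol (Section 9.4.2) leaves the handling of deaths in time-to-event analyses to the SAP, so no other text settles the matter. With 4 to 8 participants per arm, one late event can move the end of a curve visibly, and the sponsor may unblind and review these outputs.

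**Working it through.** The documents give no figure on this point, so there is none to reproduce. The check is a Kaplan-Meier calculation on constructed arms.

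**Inputs**

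- Censoring time for deaths: Day 28 (SAP Section 3; SAP 5.2 footnotes).
- Latest follow-up for survivors: 28 + 3 = Day 31 (protocol Schedule of Activities and Section 4.4; no cap in the SAP). Day 31 is inferred; the SAP does not state it.
- Arm sizes: 6 and 6 in Cohort 1. For Cohort 2, 8 and 4 in the protocol; SAP Section 2 says 6 and 6.
- Event times: illustrative.

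**Formula.** The curve shows 1 − S(t), where S(t) is the product over event times of (1 − events ÷ number at risk).

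**Arm of 8.** Discharges at 6, 8, 9, 11, 15 and 20 days, one death, one discharge at 30 days.

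- After Day 20: S = 7/8 × 6/7 × 5/6 × 4/5 × 3/4 × 2/3 = 2/8 = 0.25.
- As written, the death leaves at 28. At 30 days 1 is at risk with 1 event: S = 0.25 × (1 − 1/1) = 0, so the curve shows 100%.
- With the death held to 31, 2 are at risk: S = 0.25 × (1 − 1/2) = 0.125, so the curve shows 87.5%, the true 7 of 8.
- With everything cut at 28, the curve stops at 75.0% (6 of 8).

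**Other patterns** (late event at 29 days or more)

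| Arm | Events by Day 28 | Deaths | Late events | Still in hospital | As written | Deaths held to 31 | All cut at 28 |
|---|---|---|---|---|---|---|---|
| 4 | 2 | 1 | 1 | 0 | 100% | 75.0% | 50.0% |
| 6 | 4 | 1 | 1 | 0 | 100% | 83.3% | 66.7% |
| 6 | 3 | 2 | 1 | 0 | 100% | 66.7% | 50.0% |
| 6 | 3 | 1 | 1 | 1 | 75.0% | 66.7% | 50.0% |
| 6 | 5 | 1 | 0 | 0 | 83.3% | 83.3% | 83.3% |

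The fourth row shows the milder case. With someone left at risk, the curve is too high (0.50 × 1/2 = 0.25 event-free, against 0.50 × 2/3 = 0.333) but below 100%. The last row shows that without a late event nothing goes wrong.

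**Quartiles.** In the third row, S is 3/6 = 0.50 before the late event and 0 after it, so a 75% quartile is printed at the late event's time. With the deaths held in, S = 0.50 × 2/3 = 0.333, and that quartile is not reached.

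**Same-day tie.** Study Day 1 is the day of the first dose, so study Day 28 ends between 27 and 28 elapsed days, depending on the clock time of the dose. The SAP does not say where Day 28 falls on the elapsed scale. For positive events it imputes a missing clock time as 00:01 when censored and as 23:59 for an event. Read that way, a death censored at 27.01 days precedes a discharge at 27.99 days. An arm of 6 with four earlier discharges then ends at 100%, although no event falls after Day 28.

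**Chance of a false 100%.** Suppose every survivor eventually has the event, each participant dies with risk p and has a late event with risk q. The chance of at least one death and at least one late event is 1 − (1 − p)^n − (1 − q)^n + (1 − p − q)^n. Assume p from 5% to 20% and q from 2% to 10%; neither range comes from the documents. The chance is then 1–17% for n = 4, 3–32% for n = 6 and 5–46% for n = 8. These figures are generous, because some survivors may not have the event at all.

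**Mortality and composite.** A Kaplan-Meier estimate up to Day 28 uses only data up to Day 28. Events on Days 29 to 31 do not change it. Only the undated count rows in Tables 18 and 19 can take in events after Day 28.

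**Day 1.** For negative events a missing event time becomes 00:01. If the event falls on Day 1 and the first dose was given later than 00:01, event time minus dose time is below zero.

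**The case against.** The case for leaving this alone has real weight.

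- **Low consequence.** This SAP covers only the analysis after the Cohort 1 or 2 lock, and protocol Section 9.4 calls the presentation of those cohorts descriptive. No test is planned, and Phase 2 data do not enter the confirmatory inference. This stands and limits the importance of the point.
- **Tables mostly unaffected.** Tables 22, 24 and 25 report counts and quartiles, not the end of the curve. In the arm of 8, S reaches 0.75, 0.50 and 0.25 at Days 8, 11 and 20, so taking the first time at or below each level gives the same quartiles with or without a cut. A convention that averages at exact ties could change the upper one. Table 24 also prints the number discharged and a separate row for deaths. This stands in the main; the two-death arm of 6 shows an exception.
- **Last contact is ordinary censoring.** For mortality and the composite this is right.

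A reader might also infer more than the documents support:

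- That any death sends the curve to 100%. It takes a death, a later survivor's event and nobody left at risk.
- That the bias in the arm of 8 is 100% against 75%. That compares two horizons; on the Day 31 horizon the overstatement is 100 − 87.5 = 12.5 points.
- That the share of late visits measures the bias. With visits spread evenly over Days 25 to 31 (an assumption), 3/7 = 43% of participants would have extra days, but these matter only if an event falls in them.
- That Section 2 expressly applies data to end of study to these tables. Its phrase "however with all data collected until End of Study (EOS" describes the Section 5.1 outputs; for Section 5.2 the open horizon follows from the absence of a cap.

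**Conclusion.** The point holds for the positive-event curves. Followed exactly, the SAP lets deaths leave the risk set before the last time at which a survivor's event can count, which defeats the rule's stated aim of avoiding bias. With one death, one late event and nobody left at risk, the final value is overstated by 1/n: 25.0, 16.7 or 12.5 points for arms of 4, 6 or 8. Otherwise the overstatement can be smaller or absent, and more than one death makes it larger.

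This rests on two things: that survivors' events after Day 28 are recorded and used, which the visit window and the missing cap allow, and that such an event occurs. It affects the tail of descriptive figures and now and then an upper quartile. It does not affect a treatment test, and the mortality and composite curves up to Day 28 are sound. The change is worth making because it is cheap and the SAP already caps at 28 days for ventilator-free days.

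**What to change.** In SAP Section 3:

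1. Define the end of Day 28 on the elapsed-time scale used for the curves.
2. For clinical improvement and hospital discharge, count only events on or before that time.
3. Censor living participants without the event at the earlier of last contact and that time.
4. Censor deaths without the event at that same time, ranked after any event on the same day. State that the 00:01 imputation does not apply to them; a plain Day 28 cut would leave the same-day tie open.

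Carry this into the footnotes of Tables 22, 24 and 25 and Figures 7 to 9. Limit the event-count rows of Tables 18 and 19 to events through Day 28, to match the first row of Table 18 and the protocol endpoints worded that way.

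As a minor separate correction, where a missing event time on Day 1 is imputed as 00:01, use the later of 00:01 and the first-dose time. This should seldom arise, because the protocol asks for date and time of each change.

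Holding deaths to the end of the visit window would also remove the false 100% and would keep the later events. The Day 28 cut discards those events but does not let a late visit lengthen the curve. Participants last seen on Days 25 to 27 are still censored early under either choice.

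The cost is one paragraph in SAP Section 3, the matching footnotes and row labels, and a date filter in the programs. No data collection changes.

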4	xx (xx.x)	xx (xx.x)	xx (xx.x)	xx (xx.x)
5	xx (xx.x)	xx (xx.x)	xx (xx.x)	xx (xx.x)
6	xx (xx.x)	xx (xx.x)	xx (xx.x)	xx (xx.x)
7	xx (xx.x)	xx (xx.x)	xx (xx.x)	xx (xx.x)
8	xx (xx.x)	xx (xx.x)	xx (xx.x)	xx (xx.x)
...				
28	xx (xx.x)	xx (xx.x)	xx (xx.x)	xx (xx.x)
n	xxx	xxx	xxx	xxx
Mean	xx.x	xx.x	xx.x	xx.x
SD	xx.x	xx.x	xx.x	xx.x
Median	xx	xx	xx	xx
Q1, Q3	xx, xx	xx, xx	xx, xx	xx, xx
Min, Max	xx, xx	xx, xx	xx, xx	xx, xx

N = Number of subjects in a specific group; n = Number of subjects with data available; Percentages are based on N; SD: Standard deviation; Q1, Q3: First, third quartile; Min: minimum; Max: maximum.

Ventilator-free days are only counted through the date of early study discontinuation, study completion date or Day 28, whichever comes first. For subjects who die during the course of the study, number of ventilator-free days is defined as 0.

Page X of Y

(Notes for programmer:

Include only the categories of Days (0-28) in the table which are available in the data
)

Table 24: Time to last hospital discharge - ITT Set

	DSTAT 0.25 N=xxx	Cohort 1 PBO N=xxx	DSTAT 0.325 N=xxx	Cohort 2 PBO N=xxx
Number of subjects discharged from hospital, n (%) (a)	xx (xx.x)	xx (xx.x)	xx (xx.x)	xx (xx.x)
Kaplan-Meier estimates (b)				
Number of censored subjects, n (%) (b)	xx (xx.x)	xx (xx.x)	xx (xx.x)	xx (xx.x)
Number of subjects alive and still in hospital	xx (xx.x)	xx (xx.x)	xx (xx.x)	xx (xx.x)
Death	xx (xx.x)	xx (xx.x)	xx (xx.x)	xx (xx.x)
Time to hospital discharge (days) (b)				
25% Quartile (95% CI)	x.x (x.xx, x.xx)	x.x (x.xx, x.xx)	x.x (x.xx, x.xx)	x.x (x.xx, x.xx)
Median (95% CI)	x.x (x.xx, x.xx)	x.x (x.xx, x.xx)	x.x (x.xx, x.xx)	x.x (x.xx, x.xx)
75% Quartile (95% CI)	x.x (x.xx, x.xx)	x.x (x.xx, x.xx)	x.x (x.xx, x.xx)	x.x (x.xx, x.xx)

N = Number of subjects in a specific group; n = Number of subjects with data available; Percentages are based on N;
 (a) Subjects discharged from hospital will be counted as event.

(b) Kaplan-Meier estimates: Subjects discharged from hospital will be counted as event. Subjects who are still in the hospital or died in the hospital will be censored.

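### The ventilator-free-day formula limits only study duration to Day 28 and subtracts rounded elapsed ventilator time, so it can return values below 0 or 28 after brief ventilation

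*SAP*

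**What the plan says.** SAP section 3, under Ventilator-free days, sets the period first: "Ventilator-free days are only counted from baseline through Day 28 or end of study, whichever comes first". It then describes the quantity by status: "Ventilator-free days are all days where Ventilator/Oxygen/Medical Care Status is not equal" to invasive mechanical ventilation or ECMO.

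The same section goes on to give a formula, "Ventilator-free days are defined as: study duration - number of ventilator days", with two terms:

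- Study duration: "Date of study completion (or date of early study discontinuation) – date of first study treatment + 1". It is capped: "The maximum study duration is set to 28 days, even if study completion or study discontinuation is after 28 days".
- Ventilator days: "Ventilator days are defined as cumulative rounded number of days with Ventilator/Oxygen/Medical Care Status" equal to IMV or ECMO, divided by 24 h. Missing clock times are set to 00:01 for a start and 23:59 for a stop. No Day 28 limit and no lower bound are given for this term.

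Deaths have their own rule: "For subjects who died during the course of the study, the number of ventilator-free days will be defined as 0".

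In SAP section 5.2, the Table 23 footnote repeats the limit at discontinuation, completion or Day 28. The programmer note fixes the scale: "Include only the categories of Days (0-28) in the table which are available in the data". The Schedule of Activities in the protocol (Table 1) allows the Day 28 visit ±3 days, with ventilator use recorded up to it.

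**The concern.** The two terms have different limits and different units. The cap on study duration shows that the SAP expects records after Day 28, but the cap is not carried over to ventilator time. Ventilation on Days 29–31 is then subtracted from a total that stops at 28. Separately, study duration counts whole calendar days inclusively, while ventilator time is elapsed hours rounded to days.

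A negative value would rank a living participant below a death, would have no category row in Table 23, and would still enter the mean and minimum. A participant briefly ventilated could look the same as one never ventilated. The endpoint is a named secondary endpoint in the protocol, and this output feeds the unblinded review of cohorts of 12, where a single value shows.

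**Working it through.** **Inputs.** Formula, cap, rounding and time imputation: SAP section 3. Range 0–28: Table 23. Final visit on Days 25–31: protocol Table 1. My assumptions: hours are meant where the SAP divides a number of days by 24 h; the total is rounded once; ventilation still ongoing is counted to the clock time shown at the final visit.

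**Formula.** Ventilator-free days = min(28, final day) − round(IMV/ECMO hours ÷ 24).

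**Can the plan's 0–28 range be reproduced?** The longest possible ventilator time by the end of Day 28, 29, 30 or 31 rounds to 28, 29, 30 or 31 days. The minimum is therefore 28 − 28 = 0, 28 − 29 = −1, 28 − 30 = −2 or 28 − 31 = −3. A grid of continuous courses ending on Days 25–31 gave the same minima, with 0 for final days 25–28. With ventilator time cut at the end of Day 28, the grid stayed within 0–28 throughout. The stated range holds only with that cut, which the formula does not contain.

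**Worked courses in survivors** (D = study day). The last column counts a day as ventilated if IMV/ECMO was in place at any time on it, within Days 1–28.

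| IMV course | Elapsed days | Rounded | As written | Cut at Day 28 | Calendar days |
|---|---|---|---|---|---|
| D1 14:00 to D31 10:00 | 716 h ÷ 24 = 29.83 | 30 | −2 | 1 | 0 |
| D1 00:01 to D31 23:59 | 31.00 | 31 | −3 | 0 | 0 |
| D3 00:01 to D31 23:59 | 29.00 | 29 | −1 | 2 | 2 |
| D29 06:00 to D31 10:00 | 52 h ÷ 24 = 2.17 | 2 | 26 | 28 | 28 |
| D1 18:00 to D28 10:00 | 640 h ÷ 24 = 26.67 | 27 | 1 | 1 | 0 |
| D1 08:00 to D28 23:00 | 663 h ÷ 24 = 27.63 | 28 | 0 | 0 | 0 |
| D20 12:00 to D28 10:00 | 190 h ÷ 24 = 7.92 | 8 | 20 | 20 | 19 |
| D3 08:00 to D3 19:00 | 11 h ÷ 24 = 0.46 | 0 | 28 | 28 | 27 |
| D5 20:00 to D6 06:00 | 10 h ÷ 24 = 0.42 | 0 | 28 | 28 | 26 |

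**Negatives.** A negative value needs at least 28.5 elapsed days, hence near-continuous ventilation from about Days 1–3 with data on Days 29–31.

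**The extra day.** From hour *s* on Day 1 to hour *e* on Day 28, elapsed time is 27 + (*e* − *s*)/24 days. It rounds to 28 only if *e* is at least 12 hours later on the clock than *s*. Otherwise it usually rounds to 27, leaving 1.

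**Rounding unit.** Three separate 11-hour episodes total 33 h = 1.375 days. Rounding the total gives 28 − 1 = 27. Rounding each episode gives 28 − 0 = 28. The SAP does not say which applies.

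**The case against.** The strongest reply is that the limit is already in the SAP. The opening sentence of the paragraph and the Table 23 footnote both stop the count at Day 28, and the shell runs 0–28. A programmer reading all of this together would cut ventilator time at Day 28, and the negative values and the 26 would not arise. That does show the intent, but the line that defines the calculation does not say so, and the cut does not remove the unit mismatch.

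A second reply is that elapsed time and any-time-that-day counting are both legitimate conventions. This stands. In a simulation of ventilated survivors (assumed mean onset 3–5 days, mean duration 8–21 days, final visit Days 28–31), 83–89% of values differed from the calendar-day count. A reader might infer that most values are wrong. The figure only measures distance from one convention, which the SAP uses for status at fixed visits (Tables 20 and 21) but does not state for this endpoint. The simulation also left out final visits on Days 25–27, where no negatives occur.

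A reader might also infer that crediting survivors who are never weaned is an error. Most of that credit follows from the SAP's own definition, which counts days before intubation. In the Day 20 course, 19 of the 20 days remain under a calendar count; the mismatch adds about 1.

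Finally, the practical effect is small. Take the planning failure rates in protocol section 9.2 (20% and 9%) and assume that half of failures die. Cohorts 1 and 2, as sized in the protocol, then give 14 × 0.09 + 10 × 0.20 = 3.26 failures and about 1.6 ventilated survivors. With the simulated 0.2–4% negative and 3–7% showing 28, that is about 0.003–0.07 negative values and 0.05–0.11 participants showing 28. This also stands.

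**Conclusion.** The formula as written does not deliver the Day 28 limit or the 0–28 scale that the SAP sets for it. Literal application gives values down to −3 and lets ventilation after Day 28 reduce the count. With ventilator time cut at Day 28, two effects of the mixed units remain: 28 ventilator-free days after less than 12 hours of IMV, and usually about 1 day for a survivor ventilated from Day 1 through Day 28.

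The consequence is limited to individual values and small-cohort summaries of a secondary endpoint that protocol section 9.4 says will be presented descriptively. A reader might infer that Table 23 contradicts the primary endpoint. It does not: any ventilation is still a failure in Table 18, and the primary endpoint is unaffected. Nor do the documents support a claim about Phase 3, which has its own SAP. If the formula were carried over unchanged, the simulated arm difference would be 1.94 rather than 1.99 days, or 2.26 rather than 2.28, a shift of about 1–3% toward zero.

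The correction is worth making because a stated rule conflicts with its own limits and two programmers could produce different tables from it. The worked values rest on the assumptions listed with the calculation.

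**What to change.** In SAP section 3:

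- Restrict ventilator time to Days 1–28, or to the end of study if earlier.
- Count both terms in the same unit. One option is calendar days within Days 1–28, scoring a day as ventilated if IMV or ECMO was in place at any time that day. If elapsed time is kept instead, express both terms in it and state whether the total or each episode is rounded.
- Bound the result at 0–28.
- Leave the death rule as it is. State that days before intubation count for survivors still ventilated, so that the choice is explicit.

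The cost is a few lines of text and programming. No new data are needed, because start and stop dates and times of ventilation are already recorded (protocol Table 1, footnote e). The calendar option has a downside to acknowledge: a brief episode crossing midnight costs two days, as in the 10-hour course above, which scores 26.
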